9.0. DATA MANAGEMENT

9.1. Data Collection Table (Aim 2)

	SCHEDULE OF DATA COLLECTION			
	Eligibility and Consent Form	Baseline Assessment (week 0)	Mid- Intervention Assessment (week 3-5)	Post- intervention Assessment* (week 8± 4)
Written Informed Consent	X			
Demographics		X		
Cancer and Treatment Characteristics		X		
Qualitative Interview			Х	Х
Activity Levels (Activity Tracker)		Х		х
Exercise Habits and Readiness		Х		
Short Physical Performance Battery ^b /Virtual Short Physical Performance Battery		Х		Х
Brief Fatigue Inventory (BFI)		X		Х
Center for Epidemiologic Studies Depression Scale (CES-D)		Х		Х
Functional Assessment of Cancer Therapy-Leukemia (FACT-Leu)		Х		Х
Self-Efficacy for Exercise		X		Х
Actigraphy ^{b,d}		X		Х
Geriatric Assessment Measures • Activities of Daily Living		х		Х

 Instrumental Activities of Daily Living Fall History 6-Minute Walk Test^{b,d} Montreal Cognitive Assessment (MoCA or MOCA Blind) 		
Bioelectrical Impedance System ^{a.b,d}	X	Х
Handgrip Dynamometer ^{b,d}	X	Х
Muscle Strength Testing ^{a.b,d}	X	X
Heart Rate Variability ^{a,b,d}	X	X
Feasibility metrics		X
System Usability Scale		X
Complete blood count (from electronic medical record)	X	X
Blood samples ^b	X	X

^aIf patient elects to undergo the assessments at the cancer center instead of the Physical Exercise, Activity and Kinesiology laboratory, these assessments will not be conducted.

^bMay be omitted for patient safety (i.e., if in-person assessments are not possible)

dIf research activities are conducted at Wilmot affiliated sites, these assessments may be omitted

9.2. All hardcopy research records will be stored onsite in the URMC, in locked research files at the James P. Wilmot Cancer Center. The Cancer Center is secured with electronic key cards. Offices within the Cancer Center are again secured by key and data is kept in locked file cabinets. Electronic research records are stored on the URMC's password secured and firewall protected networks. These are the same methods of security used for patient medical records. All study data (including the electronic data kept by the PointClick Care company) will be kept for a period of 7 years after the study and all reports and publications are complete.

9.3. All data collected for the current study will be used in post hoc analyses as appropriate. Data will not be used for future studies without prior consent of the patient. The patient's individual research record will not be shared with their treating physician, unless they provide consent or the patient's treating physician is a study physician, in which case they will have access to study data as a study co-investigator. Overall study results will be presented to participants, faculty and staff at the URMC after completion of the study. Study results will be presented at professional meetings and published.

9.4. The study coordinator will assign a numerical study ID to each participant once they have signed the consent form (chronologically based on the data they signed consent i.e., 001, 002, 003...). All study forms and questionnaires will use this number and the participant's first, middle, and last initials as identifiers, to ensure data integrity. Other identifying information will not exist on these forms. A complete list of study participants with study ID, name, and contact information will be maintained separately. This linkage information will only be accessible to the study coordinator, study investigators, and the individuals responsible for maintaining the database.

9.5. Additionally, data on the socio-demographics, clinical, cancer and treatment characteristics will be collected and managed by the research teams at URMC using REDCap electronic data capture tools hosted at URMC.¹¹⁸ We will also evaluate the medical records for clinical characteristics and outcomes, and utilize REDCap to collect and manage this information.

9.5a. URMC provides the following information on the **REDCap program:** "Vanderbilt University, in collaboration with a consortium of institutional partners, has developed a software toolset and workflow methodology for electronic collection and management of research and clinical trial data, called REDCap (Research Electronic Data Capture). The REDCap system is a secure, web-based application that is flexible enough to be used for a variety of types of research. It provides an intuitive interface for users to enter data and real time validation rules (with automated data type and range checks) at the time of data entry. REDCap offers easy data manipulation with audit trails and functionality for reporting, monitoring and querying patient records, as well as an automated export mechanism to common statistical packages (SPSS, SAS, Stata, R/S-Plus). Through the REDCap Consortium, Vanderbilt has disseminated REDCap for use around the world. Currently, over 240 academic and non-profit consortium partners on six continents with over 26,000 research end-users use REDCap.¹¹⁹

9.5b. According to the Clinical and Translational Science Institute (CTSI), REDCap is supported with the following means. "The *CTSI Informatics Core*, a unit of the SMD *Academic Information Technology (AIT) Group*, will serve as a central facilitator for data processing and management. REDCap data collection projects rely on a thorough study-specific data dictionary defined in an iterative self-documenting process by all members of the research team, with planning assistance from the *AIT-CTSI Informatics Core*. The iterative development and testing process results in a well-planned data collection strategy for individual studies."¹¹⁹

9.5c. The CTSI states that regarding security, "REDCap servers are housed in a local data center at the University of Rochester and all web-based information transmission is encrypted. REDCap was developed in a manner consistent with HIPAA security requirements and is recommended to University of Rochester researchers by the URMC Research Privacy Officer and Office for Human Subject Protection.¹¹⁹

Protocol Version: 22OCTOBER2021

Page **39** of **54**

10.0. RISKS/BENEFITS

10.1. Risks

There are two potential risks associated with participation in the proposed study: 1) physical harm associated with intervention procedures, and 2) loss of confidentiality.

10.1.1. In terms of physical harm associated with intervention procedures, commencement of a moderate walking and progressive resistance exercise program is not associated with any severe side effects and risks are minimal for individuals with no cardiopulmonary, orthopedic, or age identified risk factors as determined by a physician. The absolute chance of a cardiac event among adults while engaging in vigorous exercise is one per year for every 15,000 to 18,000 people. A transient increase in blood pressure may occur with all types of exercise. Although unlikely, a low to moderate walking and progressive resistance exercise program may also cause musculoskeletal effects, such as mild muscle soreness, a muscle strain, or other related accidental injuries such as tripping. Overall, the risk level for participation in the proposed low to moderate intensity exercise program is minimal.

10.1.2. In terms of loss of confidentiality, quantitative data from participants will need to be stored. Though rigorous and well-tested data safety and security guidelines will be observed, there is still a chance that confidentiality could be breached and sensitive medical information could become known to persons outside the research team.

10.2. Benefits

Patients participating in the first aim will be paid \$30 and those participating in the second aim will be paid \$50 for their participation in the form of gift cards. For Aim 1, patients will receive the gift cards immediately following the interviews. For Aim 2, patients will be paid for completion of the post-intervention assessment. Patients in Aim 2, patients may also keep the exercise kit and activity tracker at study completion (value \$150).

11.0. DATA SAFETY AND MONITORING

Only adverse events (AEs) related to the study intervention or procedures will be reported. In other words, AEs related to cancer treatment will not be reported.

11.1. Adverse Event Reporting Requirements

11.1.1. Adverse events will be reported using the URCC Adverse Event form and/or as required by the Cancer Center Clinical Trials Office.

	Grade 1	Grade 2			Grade 3			Grade 4		Grade 5		
		Unexpected		Expected	Unexpected		Expected		Unexpected	Expected	Unexpected	Expected
	Unexpected and Expected	with hospitalizatio n	without hospital- ization		with hospitalizati on	without hospitaliza tion	with hospitaliz ation	without hospitaliz ation				
Unrelated Unlikely	Not Required	Not Required	Not Required	Not Required	Not Required	Not Required	Not Required	Not Required	10 Calendar Days	Not Required	10 Calendar Days	10 Calendar Days
Possible Probable Definite	Not Required	10 Calendar Days	Not Required	Not Required	10 Calendar Days	10 Calendar Days	Not Required	Not Required	24-Hour; 5 Calendar Days	10 Calendar Days	24-Hour; 5 Calendar Days	10 Calendar Days

11.1.2. Adverse events will be reported in accordance with the following guidelines:

11.1.3. Adverse event reports will be submitted in one of the following ways:

(1) By email: (pdf)
(2) By mail:
(3) By fax:

11.1.4. An unexpected adverse event is defined as any adverse experience, the specificity or severity of which is not consistent with the risk information. This is a minimal risk study as both exercise and mobile app-driven interventions have been shown to improve outcomes in community-dwelling older adults.

11.1.5. A serious event refers to any event in which the outcome results in any of the following: death, a life-threatening adverse experience, inpatient hospitalization or prolongation of existing hospitalization, a persistent or significant disability, incapacity, or a congenital anomaly/birth defect. Important medical events that may not result in death, be life-threatening, or require hospitalization may be considered a serious adverse drug experience when, based upon appropriate medical judgment, they may jeopardize the participant and may

require medical or surgical intervention to prevent one of the outcomes listed in this definition. We anticipate that any serious events will be related to standard of care cancer treatments and not due to the intervention. We will not collect adverse events related to cancer treatments.

11.1.6. Adverse events will be reported in accordance with institutional policies (University of Rochester, Research Subject Review Board, local IRB, URCC CCOP, CTO, and DSMB) as per their requirements.

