11.2. Data Safety Monitoring

11.2.1. All adverse events requiring reporting will be submitted to the current Project Coordinator as described in Section 11.1. Serious adverse event reports will be forwarded to the study chair and the Data Safety and Monitoring Committee (DSMC). Adverse events are entered into a protocol-specific spreadsheet.

11.2.2. Adverse event rates are monitored utilizing the spreadsheet. If a serious adverse event is reported frequently, the study chair will conduct a detailed review. The DSMC Committee Chair will be notified and will determine if further action is required.

11.2.3. The Data Safety Monitoring Committee (DSMC) will review study progress and cumulative reports of adverse events every year and as needed. An overall assessment of accrual and adverse events will enable the committee members to assess whether significant benefits or risks are occurring that would warrant study closure.

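### The Section 11.1 table exempts related, expected events with hospitalisation that Section 11.1.5 defines as serious, so such an event can go unreported to the DSMC

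*Combined protocol and SAP*

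**What the plan says.** All references are to the combined protocol and SAP.

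- **Section 11.0** limits reporting to adverse events attributable to the intervention or to study procedures. It does not exempt expected ones.
- **Section 11.1, table.** Rows are set by attribution and columns by grade, expectedness and, for some grades, hospitalisation. The related row, headed "Possible Probable Definite", runs through Grade 3 as "Possible Probable Definite Not Required 10 Calendar Days Not Required Not Required 10 Calendar Days 10 Calendar Days Not Required Not Required". Grade 1 has a single column, "Unexpected and Expected".
- **Section 11.1.4** calls an event unexpected if its nature or its severity does not fit the risk information.
- **Section 11.1.5**: "A serious event refers to any event in which the outcome results in any of the following: death, a life-threatening adverse experience, inpatient hospitalization". The list goes on to a prolonged admission and lasting disability, among other outcomes.
- **Section 11.2.1**: "All adverse events requiring reporting will be submitted to the current Project Coordinator as described in Section 11.1". Serious adverse event reports then go to the study chair and the DSMC. The same paragraph says, without qualification, that adverse events are entered in a protocol spreadsheet.
- **Sections 11.2.2 and 11.2.3**: "Adverse event rates are monitored utilizing the spreadsheet", and the DSMC looks at cumulative reports yearly, or more often if needed.
- **Section 10.1.1** names musculoskeletal effects of the programme, "such as mild muscle soreness, a muscle strain, or other related accidental injuries such as tripping".

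**The concern.** Two rules in the same section point in opposite directions for the same event. Under 11.1.5 a hospitalised event is serious, and 11.2.1 assumes that a serious event produces a report that reaches the DSMC. Under the table, a related event with hospitalisation needs no report if it is Grade 3 and expected. Site staff who follow the table cell by cell would file nothing, and there would then be no report to pass on.

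The exempted events are those that the protocol itself attributes to exercise. Participants are aged 60 or over, with ECOG status 0-2, and may use a walking aid (Section 3.4). A fall leading to admission is a realistic event in this group. Under 11.2.3 the DSMC judges from cumulative reports whether the risks justify closing the study, and under 11.2.2 the study chair's detailed review is triggered by how often a serious event is reported. Both depend on what is filed.

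**Working it through.** No sample-size or probability calculation applies. The check is a cell-by-cell reading of the table against the definitions.

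**1. Do the extracted cells line up?** The header gives 1 column for Grade 1, 3 for Grade 2, 4 for Grade 3, 2 for Grade 4 and 2 for Grade 5: 1 + 3 + 4 + 2 + 2 = 12. Each row has 12 entries, so the cells have not shifted.

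**2. Related row.**

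| Column | Entry |
|---|---|
| Grade 1, any | Not Required |
| Grade 2 unexpected, hospitalised | 10 days |
| Grade 2 unexpected, not hospitalised | Not Required |
| Grade 2 expected (no split) | Not Required |
| Grade 3 unexpected, hospitalised | 10 days |
| Grade 3 unexpected, not hospitalised | 10 days |
| Grade 3 expected, hospitalised | Not Required |
| Grade 3 expected, not hospitalised | Not Required |
| Grade 4 unexpected | 24 hours; 5 days |
| Grade 4 expected | 10 days |
| Grade 5 unexpected | 24 hours; 5 days |
| Grade 5 expected | 10 days |

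Five cells are *Not Required*, and 12 − 5 = 7 carry a deadline.

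**3. Which exempt cells conflict with 11.1.5 through hospitalisation?**

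- Grade 3 expected, hospitalised: always. Every event in this cell is serious by definition.
- Grade 2 expected: whenever the patient is admitted, because the column does not separate admitted from non-admitted patients.
- Grade 1: the same holds in principle, since this column has no split either, but an admission at Grade 1 is a remote case.
- The two exempt cells for non-hospitalised events: no conflict through hospitalisation.

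**4. Can an exercise injury fall into the first two?** By 11.1.4, an event that fits the risk information in both nature and severity is expected. Section 10.1.1 attaches *mild* to soreness but sets no severity limit on tripping injuries. It also mentions a cardiac event, but in relation to vigorous exercise, so tripping is the cleaner example. Take a patient who trips on a prescribed walk and is admitted with a Grade 3 injury. The event is related, it is serious under 11.1.5, and it can be judged expected. The table entry is then *Not Required*.

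**5. What happens next?** Section 11.2.1 submits the events that require reporting under 11.1. This one does not, so no serious adverse event report arises from that route. Section 11.0, which says that intervention-related events are reported, points the other way.

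**The case against.** The best defence has four parts.

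- **Severity.** Section 11.1.4 counts severity as well as type. Section 10.1.1 describes the programme as free of severe side effects and its risk as minimal, and 11.1.5 anticipates that serious events will come from cancer treatment. An investigator could well call an admission after a trip unexpected by severity, and the table would then require a report in 10 days. This stands as a possible outcome. It leaves reporting to a judgement that the protocol does not guide.
- **Timing only.** Every entry other than *Not Required* is a deadline, so the table may be meant to govern only individual, timed reports, with the unqualified spreadsheet sentence in 11.2.1 covering everything else. That reading is open, but the protocol does not state it or describe a separate routine route, and the sentence does not say that exempt events are logged.
- **Other channels.** Section 11.1.1 refers to the clinical trials office's requirements and 11.1.6 to institutional, review board and DSMB requirements. These may catch a hospitalised related event. Their content is not given, so this cannot be settled either way.
- **Other data.** Weekly symptom questionnaires, weekly exercise-safety questions, coordinator calls and fall history (Sections 7.1 and 7.2.3.6) mean that falls and symptoms would not vanish from the study data. No path from these to the DSMC is stated.

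A reader might go further and infer that the pilot is bound to show no adverse events, or that DSMC review cannot function. The documents do not support this: 7 of 12 related cells require a report, including all Grade 4 and 5 events and all unexpected Grade 3 events, and the spreadsheet may hold more. A reader might also see the exemption of ordinary soreness, strains and falls without admission at Grade 1-2 as contradicting 11.1.5. It does not, since those events are not generally serious. For them the only question is whether they reach the spreadsheet and the cumulative review.

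**Conclusion.** The point holds as an internal contradiction with a bounded reach. One related cell (expected Grade 3 with hospitalisation) conflicts outright with 11.1.5, and the expected Grade 2 cell conflicts whenever the patient is admitted. Both also sit badly with 11.0. Followed as written, a related, serious event can fail to reach the DSMC. This rests on two assumptions: that the event is judged expected in severity as well as type, and that no unseen institutional rule captures it.

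The documents give no rate of exercise injuries leading to admission, so the number of events affected cannot be estimated. The feasibility criteria and their confidence intervals are untouched. Because the gap concerns safety oversight and is cheap to close, the text should be changed. The handling of unrelated events is a separate question.

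**What to change.** 1. Reconcile the table with 11.0, 11.1.5 and 11.2.1, so that any possibly, probably or definitely related event meeting the 11.1.5 definition is reported and forwarded to the study chair and DSMC, whatever its grade or expectedness. Tying the rule to the definition also covers the missing hospitalisation split at Grade 2 and the other serious outcomes in 11.1.5.
2. State in 11.2.1 that the spreadsheet and the DSMC's cumulative review include related events marked *Not Required*, and that the table governs only the timing of individual reports.

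The cost is an amendment to a few sentences and one table row, a few extra log lines in a study of 25 patients, and a slightly less favourable adverse event count. No change to the analysis or sample size is needed.

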11.2. Data Safety Monitoring

11.2.1. All adverse events requiring reporting will be submitted to the current Project Coordinator as described in Section 11.1. Serious adverse event reports will be forwarded to the study chair and the Data Safety and Monitoring Committee (DSMC). Adverse events are entered into a protocol-specific spreadsheet.

11.2.2. Adverse event rates are monitored utilizing the spreadsheet. If a serious adverse event is reported frequently, the study chair will conduct a detailed review. The DSMC Committee Chair will be notified and will determine if further action is required.

11.2.3. The Data Safety Monitoring Committee (DSMC) will review study progress and cumulative reports of adverse events every year and as needed. An overall assessment of accrual and adverse events will enable the committee members to assess whether significant benefits or risks are occurring that would warrant study closure.

